2.2.3 Pharmacokynetics and Pharmacodynamics

Metformin has a poor oral bioavailability in the horse. Instead, oral bioavailability in the cat is similar to that in human. In fact, a dosage of 2 mg/Kg in the cat (equivalent to that

commonly used in human) allows to enrich therapeutic plasma levels (60). Furthermore, no pharmacokinetics differences have been found between diabetic and non diabetic cats, in whom metformin effects on glycemic control depend on basal insulin levels (61).

Absorption

After an oral dose of metformin, T_{max} is reached in 2.5 h. Absolute bioavailability of a 500 mg metformin tablet is approximately 50-60 % in healthy subjects. After an oral dose, the non-absorbed fraction recovered in faeces was 20-30 %.

After oral administration, metformin absorption is saturable and incomplete. It is assumed that the pharmacokinetics of metformin absorption is non-linear. At the usual metformin doses and dosing schedules, steady state plasma concentrations are reached within 24-48 h and are generally less than 1 μ g/mL. In controlled clinical trials, maximum metformin plasma levels (C_{max}) did not exceed 5 μ g/mL, even at maximum doses.

Food decreases the extent and slightly delays the absorption of metformin. Following administration of a dose of 850 mg, a 40 % lower plasma peak concentration, a 25 % decrease in AUC and a 35 min prolongation of time to peak plasma concentration was observed. The clinical relevance of this decrease is unknown.

Distribution

Plasma protein binding is negligible. Metformin partitions into erythrocytes. The blood peak is lower than the plasma peak and appears at approximately the same time. The red blood cells most likely represent a secondary compartment of distribution. The mean Vd ranged between 63 – 276 L.

Biotransformation

Metformin is excreted unchanged in the urine. No metabolites have been identified in humans.

Elimination

Renal clearance of metformin is > 400 mL/min, indicating that metformin is eliminated by glomerular filtration and tubular secretion. Following an oral dose, the apparent terminal elimination half-life is approximately 6.5 h. When renal function is impaired, renal clearance is decreased in proportion to that of creatinine and thus the elimination half-life is prolonged, leading to increased levels of metformin in plasma.

In humans, oral bioavailability of metformin does not differ between diabetics and non diabetics, nor between men and women; it is reduced by concomitant assumption of food and it does not proportionally increase as dosage increases (61).

Plasma levels of metformin are mainly influenced by age and eGFR (62–64), than by OCT (Organic Cations Transporter) polymorphisms. In fact, Duong and coll. (63) have demonstrated that, in order to avoid MALA onset, metformin plasma levels have to be lower than 2,5 mg/l, thus it is useful to adapt metformin dosage to eGFR, avoiding to overcome these ratios: 500 mg of metformin if eGFR lower than 15 ml/min, 1,000 mg if eGFR <30 ml/min, 2,000 mg if <60 ml/min, 3,000 mg if <120 ml/min.

Diuretics (65,66), even if able to induce eGFR reduction because of dehydration, are not able "per sè" to reduce metformin clearance, unlike proton pump inhibitors. As they block OCT (67).

Even if metformin is excreted un-modified by the kidney, liver failure can itself reduce metformin excretion, thus increasing metformin toxicity (68).

Metformin effects on glycemic control are directly proportional to basal glucose and insulin levels; in fact in healthy individuals metformin has no influence on fasting glucose levels, but significantly reduces after-meal insulin levels (69).

Metformin activates AMPK (AMP dependent Protein Kinase) in a dose dependent manner, thus causing forced inhibition of mTOR (mammalian Target of Rapamycin) and CFTR (Cystic Fibrosis Transmembrane conductance Regulator).

Very recent published data suggests that the mechanism of action of metformin in vivo may involve pathways other than those related to AMPK. It is critically important to determine whether the potential therapeutic effects of metformin that has been identified in the context of ADPKD are due to its capacity to activate AMPK or are, instead, due to its effects on other targets.

Recent research indicates that metformin can decrease cellular levels of cAMP. This is especially relevant in the setting of ADPKD because a substantial body of research has demonstrated that elevation of cAMP promotes cyst growth in vitro and in vivo. Furthermore, drug therapies that reduce cAMP are able to slow cyst growth both in mouse models of ADPKD as well as in human ADPKD patients (70).

A recent paper from the group of [name] reported that cells homozygous for ADPKD-causing mutations feature substantial perturbations in energy production (71). These cells exhibit very high levels of glycolysis and low levels of oxidative metabolism, reminiscent of the Warburg effect that is seen in tumor cells. As a result of the very high levels of glycolysis the cytoplasmic levels of ATP are very high and levels of active AMPK are consequently very low. These data further support the idea that small molecule AMPKactivators may have therapeutic benefit in ADPKD.

2.2.4 Justification for the route of administration, dosage and dosage regimens

Dose choice has been done on the basis of Takiar et al. study (7). They examined *"in vivo"* only one dose known to activate AMPK (daily i.p. injections of metformin 300 mg·kg⁻¹·d⁻¹ dissolved in a 5% dextrose solution). When considered on a simple milligram per kilogram body weight basis, this dose appears considerably higher than the current maximum dose

prescribed for patients with diabetes or polycystic ovary syndrome. However, humanequivalent dose extrapolation is calculated more accurately based on body surface area than on weight. When this calculation is performed for a 60-kg adult, the dose used in our mouse studies extrapolates to a daily dose of ~1,500 mg (7), well within the range in which metformin is safely used in humans.

After oral administration, metformin absorption is saturable and incomplete. It is assumed that the pharmacokinetics of metformin absorption is non-linear. For this reason, a split doses regimen has been chosen for metformin administration (one cap every eight hours).

Patients randomized to tolvaptan, will start the treatment according to AIFA indications (45 mg followed, 8 hours later, by 15 mg), then they will up-titrate (every week, if tolerated) to 60 mg + 30 mg and then to 90 mg + 30 mg.

Patients on metformin, will start to take metformin once a day (500 mg), between meals. Every week they will up-titrate to 500 mg twice a day (if tolerated) and then to 500 mg thrice a day.

2.3 Rationale of the study

Renal cyst development and expansion in ADPKD involves both fluid secretion and abnormal proliferation of cyst-lining epithelial cells. The chloride channel of the cystic fibrosis transmembrane conductance regulator (CFTR) participates in secretion of cyst fluid, and the mammalian target of rapamycin (mTOR) pathway may drive proliferation of cyst epithelial cells. CFTR and mTOR are both negatively regulated by AMP-activated protein kinase (AMPK). Metformin, a drug widely used, is a pharmacological activator of AMPK. We found that metformin stimulates AMPK, resulting in inhibition of both CFTR and the mTOR pathways. Metformin induces significant arrest of cystic growth in both in vitro and ex vivo models of renal cystogenesis. In addition, metformin administration produces a significant decrease in the cystic index in two mouse models of ADPKD. These results suggest a possible role for AMPK activation in slowing renal cystogenesis as well as the potential for therapeutic application of metformin in the context of ADPKD.

Currently three randomized clinical trial are evaluating Metformin effectiveness in slowing ADPKD progression.

A phase II, double-blinded randomized placebo-controlled trial ("TAME" study – NCT02656017) of 26 months duration will include non diabetic adults (n = 96) aged 18-60 years, with an eGFR \geq 50 mL/min/1.73 m2 and ADPKD, recruited from university-based practices in Baltimore and Boston. Participants will be randomized in 1:1 ratio to metformin or placebo at 500 mg once daily, increased every 2 weeks to a maximum of 1,000 mg twice daily as tolerated. Dose is decreased if eGFR falls to 30-45 mL/min/1.73 m2 and discontinued at eGFR < 30 mL/min/1.73 m2.

The primary outcomes are safety, assessed by the rates of hypoglycemia, elevated lactic acid levels, adverse events, and tolerability assessed by the Gastrointestinal Severity Rating Scale and maximum tolerated dose of study medication. Secondary outcomes include changes in total kidney and liver volumes, pain, and health-related quality of life, and changes in urinary metabolomics biomarkers (72).

Another phase II double-blinded randomized placebo-controlled trial – NCT02903511 –of 12 months duration will include non diabetic adults (n = 50) aged 30-60 years, with an estimated glomerular filtration rate (eGFR) between 50-80 mL/min/1.73 m² and ADPKD, recruited from university-based practices in Denver. Participants will be randomized in 1:1 ratio to metformin or placebo at 500 mg once daily, increased every 2 weeks to a maximum of 1,000 mg twice daily as tolerated.

The primary outcomes are safety, assessed as percentage of participants who at the end of 12 months are still prescribed the full-randomized dose of metformin, and the percentage of participants who are prescribed at least 50% of the randomized dose. Secondary outcomes include changes in total kidney volume measured by MRI at baseline and 12 months, Change in kidney function calculated from serum creatinine measurements at baseline and after 3, 6, 9 and 12 months, Rate of Serious Adverse Events (73).

Moreover a Dutch cross-over clinical trial will evaluate metformin efficacy in attenuating aquaretic effects of tolvaptan (74)

2.4 Population of the Study

This trial will enroll approximately 150 tolvaptan and metformin naïve subjects affected by Type I-truncating ADPKD, as they have grater probability of progression (10). Moreover data from Tempo trials (3/4 and 4/4) (19,75) and from its post-hoc analysis (76) revealed that patient with faster disease progression had greater beneficial effects from therapy.

Male and female adults will be enrolled, from 18-50 years of age with eGFR greater than $45 \text{ ml/min}/1,73 \text{ m}^2$

The study will be conducted in 11 Hospital Nephrology Departments. Patients will be selected from local databases and subjects will be enrolled till the estimated sample size is achieved.

Only subjects tolerating a run-in period of tolvaptan or metformin will enter the ontreatment period, in order to limit subsequent withdrawal due to lack of tolerability.

3. OBJECTIVES

Objective of the study is to assess if a two-year course of 1500 mg oral metformin is effective and safe in treatment of ADPKD, as compared to the actual gold-standard therapy, tolvaptan (Jinarc®).

3.1 Primary objectives

Currently, drugs' efficacy in ADPKD has been evaluated by means of eGFR and TKV variations. In ADPKD, kidney function may remain preserved until the 4th to 6th decade of life, when advanced renal cystic involvement has occurred. In fact, measured GFR is a poor marker of disease severity and progression, especially in early phases, when it is preserved through compensatory hyperfiltration during a prolonged period (typically decades), but eventually declines sharply. Despite this, to date, eGFR remains the standard to assess kidney function in randomized clinical trials in ADPKD. By contrast, TKV in relation to age can identify patients with progressive disease. TKV is an accurate estimate of kidney cyst burden and associates with pain, hypertension, gross hematuria, proteinuria or albuminuria, and loss of kidney function. TKV increases exponentially in virtually every ADPKD patient, with an average of 5–6%/year in adults. Elevated TKV, particularly when used together with age and kidney function, identifies individuals who are at higher risk for progression to ESRD. Precise measurement of TKV is necessary in clinical trials to assess the impact of therapeutic interventions over short periods of time and can be obtained by planimetry or stereology analysis of CT images.

3.2 Secondary objectives

Main secondary objective is to assess metformin efficacy (as compared to tolvaptan) in reducing the increase of TKV.

Moreover, it will be evaluated the rate of onset of metformin and tolvaptan related Adverse Events (AEs) namely Metfromin Associated Lactic Acidosis (MALA) and Acute Liver Injury (ALI), respectively.

4. TRIAL DESIGN

This is a phase 3a, independent, multi-centre, parallel arms, randomized controlled trial comparing efficacy and safety of metformin and tolvaptan in ADPKD. The overall design is illustrated in figures 1,2,3,4.

Each investigator has both ethical and legal responsibility to ensure that subjects being considered for inclusion in this trial are given a full explanation of the protocol and of their role and responsibilities in the proposed research. This will be documented on a written ICF that shall be approved by the same institutional review board/independent ethics committee (IRB/IEC) responsible for approval of this protocol. In addition, the protocol explanation may include recorded or electronic means of education, which will also meet IRB/IRC approval. Each ICF will include the elements required by the International Conference on Harmonization (ICH) Good Clinical Practice (GCP) Guideline and local regulatory requirements and must adhere to the ethical principles that have their origin in the Declaration of Helsinki. Subject insurance and the publication policy for the trial will be provided and documented according to DM 14 Luglio 2009.

Written informed consent will be obtained from all subjects (or their guardian or legal representative, as applicable for local laws). Investigators may discuss the availability of the trial and the possibility for entry with a potential subject without first obtaining consent. However, informed consent must be obtained and documented prior to initiation of any procedures that are performed solely for the purpose of determining eligibility for this trial,

including withdrawal from current medication(s). When this is done in anticipation of, or in preparation for, the research, it is considered to be part of the research.

Once the appropriate essential information has been provided to the subject and fully explained in layman's language by the investigator (or a qualified designee) and it is felt that the subject understands the implications of participating, the IRB/IEC-approved written ICF shall be personally signed and dated by both the subject and the person obtaining consent (investigator or designee), and by any other parties required by the IRB/IEC. The subject shall be given a copy of the signed ICF; the original shall be kept on file by the investigator. All of the above mentioned activities must be completed prior to the subject's participating in the trial. Every phase of the trial will be conducted in compliance with the protocol, GCP and the applicable regulatory requirement.

The trial contemplates a **2 weeks screening period** (included in a 9 months total recruitment period) during which 3 visits have to be collected (the 1st and the 2nd in three days, and the 3rd after biochemical analyses performed during the first two visits have been reviewed). The subject's eligibility for the trial will be confirmed by the mean of eGFR calculated from the 2 pre-treatment, central-lab, serum creatinine assessments. Longer screening periods (up to 4 additional weeks) are acceptable for subjects needing stabilization after changing or discontinuing other treatments, especially anti-hypertensives and diuretics. In this case Subjects must sign ICF and then agree to be switched to an alternate form of therapy in order to be eligible. As part of this stabilization or wash-out period different lab safety tests may be performed. Subjects who fail to meet trial requirements during the screening period may be rescreened at a later date.

Once eligibility is assessed, patients will undergo non-contrast enhanced CT-scan of kidneys (if not performed within six months prior to randomization).

Randomization visit will occur on Day -29. During this visit patients will be randomized (in a ratio 1:1 tolvaptan:metformin) to each arm of treatment and will start an **IMP titration period** (3 weeks from -28 to -8). Subjects not tolerating the minimum IMP dose will be considered "Titration failures" and will complete End of Treatment (EoTx) visit assessments and will be followed up after 7 days by phone call to assess any ongoing AEs. Subjects tolerating the minimum IMP dose enter the unblind **run-in period** (1 week from Day -7 to -1). During the "Run-in" phase, subjects will continue on a stable IMP dose to confirm tolerability over a longer period. At the end of the run-in period (Day -1), subjects not tolerating the minimum IMP dose will be considered "Run-in failures" and will complete EoTx visit assessments and will be followed up after 7 days by phone call to assess any ongoing AEs. Subjects completing the run-in will start the open-label **24 months treatment period**, during which visits will be collected three-monthly. At the end of the 24th month, and in case of early treatment cessation, **follow-up period** (3 weeks from +8 to +21) will start, during which 2 visits have to be collected. No IMP will be administered during this period.

Assessments at the Randomization (Day -29), End of IMP Run-in Period (Day -1), End of each three-monthly of on-therapy period will include those for points 2 to 8 of screening period plus IMP dispensation.

Assessments during EoTx Visits (in case of Titration failure, Run-in failure, early treatment cessation) and Follow-up visits will include those for points 2 to 8 of screening period. Non contrast enhanced CT-scan of the kidneys for TKV measurement will be also performed at the end of Month 24.

Patients treated with tolvaptan, will anyhow undergo monthly visits during the first 18 months of therapy (as prescribed by the additional monitoring requested by AIFA), then every three months.

4.1 Screening Period (up to Day -30)

No investigational treatments will be administered during the screening period.

Preliminary eligibility for the trial will be initially assessed using the subjects' historical laboratory or imaging data.

During this period, the subject's eligibility for the trial will be confirmed using historical genetic test data and imaging data of the kidneys to support a diagnosis of ADPKD and to verify the level of CKD primarily due to ADPKD and not to other renal (hypoplasia) or metabolic (diabetic or hypertensive nephropathy) disorders.

Eligibility will be confirmed by the mean of eGFR calculated from the subjects' 2 pretreatment, central-lab, serum creatinine assessments (collected at least 24 hours apart). The final screening visit on Day -29 will not be scheduled until laboratory results from the second screening visit (V2) are received and evaluated. The eGFR values will be estimated based on the Chronic Kidney Disease-Epidemiology (CKD-EPI) formula. Subjects will be told that they will receive tolvaptan or metformin during the subsequent periods of the trial.

On Day -30, patients will undergo TKV measurement by means of Ct- or MRI-scan (if not already performed within the 6 months before the enrollment). Then, patients will be randomized to receive either metformin or tolvaptan and they will be told to start IMP assumption since the day after randomization.

Those randomized in metfromin arm will receive Zuglimet® 500 mg (2 packages, each of them containing 3 blisters; every blister contains ten 500 mg coated tablets).

Those randomized to tolvaptan arm will receive Jinarc® 45/15 mg (2 packages, each of them containing 4 blisters; every blister contains seven 15 mg tablets of and seven 45 mg tablets).

The screening period will last 1-2 weeks, but may be extended up to an additional 8 weeks for subjects who require modification of medical care or further medical evaluation specifically for this trial. This may include, for example, stabilizing anti-hypertensive regimens for subjects discontinuing diuretics or "wash-out" of other investigational agents.

4.2 Randomization visit (Day -30)

Randomization process will be carried out by a WEB-based, internet-accessible, system (e-trial platform). Investigators willing to include a patient should log-in into the e-trial platform and complete the registration form.

The patient allocation number and the treatment arm will be immediately TRASMITTED on line without blinding.

Any controversial eligibility assessment will be discussed with the Study Chair.

Each patient will be informed via a cover letter including clear instructions on participation, drug use, dosing and prescription.

Randomization visit may coincide with CT-scan visit.

4.3 IMP Titration Period (since Day -28 up to Day -8)

Subjects randomized in tolvaptan arm will be given a split dose of 45/15 mg tolvaptan (unblind) with upward titration every 7 days to 45/15 mg, 60/30 mg, up to a maximum dose

of 90/30 mg per day over 3 weeks. Jinarc® has to be taken between meals; the first dose upon waking and the second dose after eight hours from the first.

Dose up-titration will be done after tolerability check (by phone call the patient will be asked: "Are you having troubles taking this drug? Are you able to tolerate this dose for the rest of your life?"). Up-titration will be done the day after tolerability check, in Day -22 and in Day -15.

Subjects who are unable to tolerate at least 45/15 mg of daily tolvaptan will be considered "Run-in failures" and will complete an EoTx visit and be followed up after 7 days by phone call to assess any ongoing AEs.

Subjects randomized to metformin arm will be given a single dose of 500 mg of metformin for the first week (unblind), then a split dose of 500/500 mg metformin with upward titration after 7 days to 500/500/500 mg, (that is the maximum trial dose of metformin per day). Zuglimet® has to be taken between meals; the first dose upon waking, the second and the third daily dose after eight hours from the previous dose.

Dose up-titration will be done after tolerability check (by phone call the patient will be asked: "Are you having troubles taking this drug? Are you able to tolerate this dose for the rest of your life?"). Up-titration will be done the day after tolerability check, in Day -22 and in Day -15.

Subjects who are unable to tolerate at least 500/500 mg of daily metformim will be considered "Run-in failures" and will complete an EoTx visit and be followed up after 7 days by phone call to assess any ongoing AEs. Subjects tolerating the minimum IMP dose will enter the unblind run-in period (1 week from Day -7 to -1).

Assessments during up-titration phone call will include:

1) Assess IMP tolerability

2) Assess AEs, if reported

4.4 IMP Run-in Period (since Day -7 up to Day -1)

Subjects tolerating at least 45/15 mg tolvaptan or 500/500 mg metformin may enter the unblind, run-in period (1 week duration). Subjects will continue on a stable IMP dose to confirm tolerability over a longer period.

At the end of the run-in period, subjects not tolerating at least 45/15 mg tolvaptan or 500/500 mg metfromin will be considered "Run-in failures". They will complete EoTx visit assessments and be followed up after 7 days by phone call to assess any ongoing AEs.

Subjects found ineligible to be randomized and continue in this trial must have a 7-day follow-up visit.

4.5 Unblind Treatment Period (Day 0 to Month 24)

Only subjects completing the IMP run-in period tolerating at least 45/15 mg of tolvaptan and 500/500 mg of metformin will be allowed upon entry to this unblind period.

In the metformin arm, during the treatment period visits will be scheduled every 3 months (each month has 28 days duration), within 3 days of the end of the trimester.

In tolvaptan treated patients, visits will be performed every month for the first 18 months, then every three months (each month has 28 days duration), within 3 days of the end of the month or the trimester (as prescribed by the additional monitoring requested by AIFA).

Beside the clinic visit and dispensing new bottles of IMP, subjects will have blood drawn on the last day of this period for efficacy and safety measures. The treatment duration of these subjects will be 24 months from the end of IMP run-in. Subjects not continuing in this trial will complete EoTx visit assessments and be followed for 7 days to assess any ongoing AEs.

From that point forward, every effort to maintain adherence and continuation of the subjects until the end of the trial should be undertaken. If continued tolerability becomes an issue, subjects may temporarily interrupt treatment as needed.

All subjects have the right to withdraw their consent from further participation in the trial at any time without prejudice.

Regardless of discontinuation of IMP, the subjects are expected to complete all monthly visits and assessments including the Month 24 visit.

4.6 Follow-up Period (up to Day +21 since Month 24 or End of Treatment)

Randomized subjects will enter the follow-up period after they complete the unblind, randomized treatment period, or after their EoTx visit, if they discontinued IMP. The follow-up period will be for 21 days in duration.

There will be no scheduled visits/assessments during the first week of the follow-up period. After the first week, 2 visits should be scheduled during the remaining 2 weeks of the follow-up period (between Day +8 and Day +21). The first visit should be scheduled on approximately Day +8, the second visit on approximately Day +21. These visits will be clinic visit.

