8.2 Safety Endpoints

They include:

- changes from baseline in creatinine;
- vital signs;
- laboratory values including liver function tests, rate of aquaretic AEs, thus including serum sodium, rate of Metformin Associated Lactic Acidosis, blood insulin and glucose levels, HOMA test in both treatment groups.

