10.5 Assessment of Liver Symptoms, Signs or Test Abnormalities

Testing for hepatic transaminase (ALT/AST), alkaline phosphatase, and BT will be performed during screening visits. Testing for hepatic transaminase (ALT/AST) will be performed during run-in and at each monthly visit in the tolvaptan arm, whereas it will be performed during three monthly visits in the metformin arm.

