10.5.1 Requirements for Repeated Liver Testing

10.5.1.1 Repeated Liver Testing in Subjects with Normal Values at Screening

The appearance of any suspicious symptom or sign should trigger prompt testing of hepatic function (i.e., within 72 hours). Local laboratory testing is acceptable, ideally with a concurrent central laboratory sample for confirmation.

Any transaminase or bilirubin values which exceed 2 x ULN should also prompt immediate retesting within 72 hours. While values remain in an abnormal range, testing frequency should be increased to at least weekly for the first month, gradually returning to monthly/three monthly as indicated by the results.

Subjects exhibiting such an increase during the tolvaptan titration/run-in phases will be disqualified from randomization on safety grounds and should not be randomized.

Should the cause of the abnormality be determined to be unrelated to tolvaptan exposure (e.g., having identified a plausible alternative explanation) such a subject may be rescreened only with medical monitor approval.

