12.3 Statistical Methods

A comparative analysis for the primary outcome will be carried out under the principle of "intention-to-treat" and including data from all subjects who are randomized. The efficacy and safety of compared interventions will be assessed. Trial data will be summarized by the calculation of means and standard deviations for normally distributed variables, medians and interquartile ranges for non-normally distributed variables, and frequency and percentage for categorical variables. Missing data will be ignored. The primary and secondary outcomes, namely the slope of the annualized eGFR and TKV will be analyzed using standard statistics including linear mixed-effects models. A P value <0.05 will be deemed significant.There are no plans for interim analyses.

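### If liver testing follows the arm-specific schedule, short silent transaminase rises are more likely to be recorded on tolvaptan than on metformin, and Section 12.3 makes no allowance for it

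*Combined protocol and SAP*

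**What the plan says.** Section 4.5 sets two visit schedules. For tolvaptan: "In tolvaptan treated patients, visits will be performed every month for the first 18 months, then every three months". For metformin: "In the metformin arm, during the treatment period visits will be scheduled every 3 months". Section 4 repeats the tolvaptan schedule, and both sections attribute it to the additional monitoring that the Italian regulator requires.

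Section 10.5 ties transaminase testing to those schedules: "at each monthly visit in the tolvaptan arm, whereas it will be performed during three monthly visits in the metformin arm". Section 10.5.1.1 fits this reading, since increased testing after an abnormal value ends by "gradually returning to monthly/three monthly as indicated by the results".

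Other sentences point towards monthly testing for everyone. Section 10.3 has liver panels analysed monthly during treatment and names no arm. Section 9.1.6.1 refers to monthly blood draws. Section 4.5, on subjects who stop study drug, says that "the subjects are expected to complete all monthly visits and assessments including the Month 24 visit". Figure 1 shows the panel containing AST and ALT only at the three-monthly columns M3 to M24.

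On use of the data, Section 8.2 lists "laboratory values including liver function tests" among the safety endpoints. Section 12.1 promises a full benefit-harm assessment of the two interventions. Section 12.3 says: "The efficacy and safety of compared interventions will be assessed". None of these addresses unequal testing.

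**The concern.** A laboratory abnormality without symptoms is recorded only if blood is drawn while it lasts. If one arm is sampled every 28 days and the other every 84 days, the first will record more short-lived rises even when the drugs have the same effect on the liver. A raw table of patients with raised transaminases would then mix drug effect with testing frequency.

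The distortion works against tolvaptan, and so in favour of metformin, on the liver risk that the protocol itself names for tolvaptan. A reader of the final report could not separate the two sources without knowing how many tests each arm had and at which visits the abnormal values were found. The trial is open-label and the schedules differ by design, so blinding offers no protection.

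**Working it through.** The plan states no visit total and no detection rate, so there is no figure of its own to reproduce.

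**Inputs from the documents.** Treatment lasts 24 months of 28 days, 24 × 28 = 672 days (Section 4.5). Allocation is 1:1 with 150 planned, so 75 per arm (Sections 4 and 12.1).

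**Visits.** Tolvaptan: months 1 to 18, then 21 and 24, 18 + 2 = 20. Metformin: 24/3 = 8, matching the eight on-treatment columns of Figure 1. At 75 per arm, scheduled tests are at most 75 × 20 = 1,500 v 75 × 8 = 600. These are ceilings, because subjects who fail titration or run-in are tested less.

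**Chance that a silent rise meets a scheduled test.** Assume that onset is uniform over 672 days and that the rise lasts d days. An onset is caught if the next test is no more than d days away, so detection = Σ min(gap, d) / 672 over the gaps between tests. Tolvaptan has 18 gaps of 28 days and 2 of 84; metformin has 8 of 84.

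| d (days) | Tolvaptan | Metformin | Ratio |
|---|---|---|---|
| 14 | 280/672 = 42% | 112/672 = 17% | 2.5 |
| 28 | 560/672 = 83% | 224/672 = 33% | 2.5 |
| 42 | 588/672 = 88% | 336/672 = 50% | 1.75 |
| 56 | 616/672 = 92% | 448/672 = 67% | 1.38 |
| 70 | 644/672 = 96% | 560/672 = 83% | 1.15 |
| 84 or more | 100% | 100% | 1.0 |

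In months 19 to 24 the arms are equal, so the whole difference arises in months 1 to 18. Simulating the 3-day visit window of Section 4.5 changes little: about 80% v 33% at 28 days, and just under 100% v about 99% at 84 days.

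**Patients found, identical drugs.** Assume that 10% of 75 per arm have one rise; this risk is not in the documents. At 28 days, 75 × 0.10 × 0.833 = 6.25 v 75 × 0.10 × 0.333 = 2.5. At 56 days, 6.88 v 5.0. With risks of 5% and 20% the 28-day figures are 3.1 v 1.25 and 12.5 v 5.0.

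**Chance of a nominally significant difference with no drug effect.** Section 12.3 names no test for this, so I used a pooled two-proportion z-test, two-sided 5%, with exact binomial probabilities.
- One rise per affected patient, risk 5%, 10% or 20%: 12.6%, 25.6%, 49.0% at 28 days; 6.2%, 9.0%, 13.5% at 56 days.
- Per-test flags correlated within patient (beta-binomial), flag chance 1% to 5%: 7.6% to 19.2% at correlation 0.3; 5.2% to 10.0% at 0.5; 3.2% to 6.6% at 0.7.

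**Restricting to common visits.** On M3 to M24 alone, a 28-day rise is found with probability 224/672 = 33% in either arm. But Section 10.5.1.3 provides for interruption after some rises. Suppose that a rise found at any tolvaptan visit clears before the next one. A common visit then records it only if it is the first visit after onset. That applies to 6 of the 18 monthly gaps and both 84-day gaps: (6 × 28 + 2 × min(84, d)) / 672. For d = 56 this is 280/672 = 42% v 67% on metformin; for d = 84, 336/672 = 50% v 100%. The restricted table can therefore err in the opposite direction.

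**The case against.** The strongest objection is that Section 10.3 already makes liver panels monthly for everyone. If it governs, the imbalance disappears. It sits badly with the arm-specific text of Section 10.5, with the absence of monthly metformin visits in Section 4.5 and with Figure 1, but the documents do not settle the matter. The point is therefore conditional.

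The reach is also limited. Section 10.5.1.1 requires prompt testing for suspicious symptoms in either arm, so only silent rises are affected, and those of about 84 days or longer are found almost equally.

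Several stronger readings are tempting and should not be drawn:

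- *That Section 3.2 plans a between-arm comparison of acute liver injury.* It names the "rate of onset of metformin and tolvaptan related Adverse Events (AEs) namely Metfromin Associated Lactic Acidosis (MALA) and Acute Liver Injury (ALI"), but the closing word of the sentence assigns each event to its own drug in turn. Support for a comparison comes only from Sections 8.2, 12.1 and 12.3, in general terms.
- *That SAE counts are inflated by testing frequency.* Section 10.1.3 lists transaminases above five times the upper limit as serious. Section 10.1.10, however, does not make an isolated grade 4 laboratory value reportable unless the investigator judges that it meets the ICH criteria, while referring back to 10.1.3. The effect on SAE counts is uncertain.
- *That every distortion runs against tolvaptan.* Sections 10.5.1.1 and 10.5.1.2 disqualify subjects with rises during tolvaptan titration or run-in, and name no metformin equivalent. Section 10.5.1.1 is worded as though randomization were still to come, but Sections 4 and 4.2 place it before titration. Removing these subjects after allocation can lower the later tolvaptan count.

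The heavier monitoring on tolvaptan is a regulatory requirement and is not in dispute. The gap is in the analysis.

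**Conclusion.** The point stands in conditional form. If Section 10.5 governs, scheduled ALT/AST testing is 20 v 8, and Section 12.3 leaves a raw liver-safety comparison open to a detection difference of up to 2.5-fold for silent rises of 28 days or less. The difference shrinks to nothing at about 84 days. The detection shares rest only on the schedule, uniform onset and the duration shown.

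A reader might infer that false-positive liver findings are likely. The documents give no rise duration, risk or within-patient correlation, and the calculated rates run from about nominal to 49% depending on those assumptions, so no single rate should be cited. Nor does the liver point touch the primary endpoint; it concerns the safety side of the benefit-harm comparison. The net direction across the whole trial is not certain either, because post-randomization disqualification on tolvaptan works the other way.

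**What to change.** 1. Reconcile Sections 10.3 and 10.5, together with the monthly wording in Sections 4.5 and 9.1.6.1, so that it is clear which liver tests are done in which arm and when.
2. In Section 12.3, pre-specify that liver-test abnormalities are tabulated over all visits with the number of tests per arm, beside a sensitivity table restricted to the visits common to both arms (M3 to M24).
3. Mark events, including laboratory-defined SAEs and treatment interruptions, that were first found at an extra tolvaptan visit. Visit dates suffice for this.
4. Count subjects disqualified for liver rises after randomization in their allocated arm.
5. State in advance that the all-visit table can overstate a tolvaptan excess and the common-visit table can understate it, and that a difference is attributed to the drugs only if both agree in direction. Agreement is a minimum condition, not proof.

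Monitoring is unchanged and all visits stay in the safety tables. The cost is one added table, one derived marker and a reconciled schedule. The common-visit table sees only about a third of 28-day rises in either arm and can miss tolvaptan rises that clear after an interruption; both limits should be stated with it.
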